A single-center, double-blind, parallel-group, placebo-controlled randomized trial.

B. Outcomes

1) Primary outcome:

- i. Presence of ischemic stroke or TIA (Transient Ischemic Attacks) assessed by symptom history during one-year follow-up and measured by number of patients in each group.
- ii. Presence of other cerebro-cardiovascular morbidity or mortality assessed by aggravation of patient status (mRS, modified Rankin Scale) at out-patient clinic during one-year follow-up and measured by the number of patients.

2) Secondary outcome:

- i. Changes in volumetric blood flow (ml/Sec) in quantitative MRA measured

by percentage change from the baseline study.

- ii. Changes in velocity (cm/Sec) in quantitative MRA measured by percentage change from the baseline study.
- iii. New FLAIR MR lesions assessed on one-year follow-up MRI and measured by the number of patients.

C. Sample size calculation

Assuming the proportion of 0.1 in the ginseng group and the proportion of 0.4 in placebo group in the analyses of primary and secondary outcomes, calculated sample size would be 29 patients each group for determining difference between two groups in the level of alpha of 0.05, power of 0.8 and 1:1 sampling ratio (equality test).

D. Randomization and follow-up of outcomes

There are two study groups as follows: a ginseng group as an intervention group, a promising placebo group as a control group. The participants will be randomly allocated to either the ginseng group or the placebo group by 1:1 ratio according to random permuted block with a block size of 20. Both groups will be followed up at 1, 3, 6 and 12 months after randomization. At each follow-up, history of the primary outcome, any adverse effects, any co-administration drugs, and study drug compliance will be evaluated. The secondary outcomes will be evaluated by comparison of the results of quantitative MR angiography studies performed at baseline and 12 months after randomization.

E. Study drugs and administration

Two study drugs are identical in appearance. In the intervention group, 2-gram ginseng per day (0.5 grams/capsule, 2 capsules twice a day) will be administrated for

12 months. In the control group, 2-gram placebo per day (0.5 grams/capsule, 2 capsules twice a day) will be administrated for 12 months.

F. Safety evaluation and reporting

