If any adverse effects are occurred, the participants will report the problem to an investigator. The investigator will appoint outpatient clinic. When the subject visits the outpatient clinic, the investigator will evaluate allergic symptoms such as redness, swelling, respiratory difficulty and grade the symptom severity. The investigator will gather other subject symptoms as patient says.

G. Primary outcome evaluation

The presence of any cerebral ischemic symptoms is the primary outcome. The history of cerebral ischemic symptoms includes transient ischemic attack (TIA) and cerebral ischemic infarction. If the related history is reported, a diffusion-weight MRI will be performed. It will be evaluated whether new ischemic lesion is related to the steno-occlusive lesion confirmed by cerebral angiography at baseline.

H. Secondary outcome evaluation

A quantitative MR angiography (QMRA) with noninvasive optimal vessel analysis (NOVA) will be performed for evaluating secondary outcomes at baseline and 12 months after randomization. QMRA with NOVA will measure blood flow at the predetermined sites. The results would become an indirect measurement of collateral flow state of a steno-occlusive vascular lesion.

8. Data collection forms and items

Subject No.	Sex	Age	Results of cerebral catheter angiography			The presence of acute ischemic lesions
			The presence of a steno-occlusive lesion at internal carotid artery, middle cerebral artery, and vertebrobasilar system	Stenosis severity (Severe/moderate/mild)	Complete total occlusion	

Medication Information				
Duration (mo)	Dose	Date Start	Date End	Compliance

※ Compliance

Drug name	Expected administration days	Actual administration days	Compliance (%)
Ginseng			
Placebo			

Non-invasive Optimal Vessel Analysis (NOVA) (at baseline)	Non-invasive Optimal Vessel Analysis (NOVA) (at 12 months after randomization)

Brain-MRI (New lesions on FLAIR) (at baseline)	Brain-MRI (New lesions on FLAIR) (at 12 months after randomization)

The presence of any ischemic stroke history at 3 months follow-up	The presence of any ischemic stroke history at 6 months follow-up	The presence of any ischemic stroke history at 9 months follow-up	The presence of any ischemic stroke history at 12 months follow-up

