The follow-ups can be conducted in outpatient clinics or by telephone interview performed by experienced nurses since the presence of ischemic stroke or TIA history is asked, and mRS is evaluated in the interview. The investigators can do neurologic evaluations if needed.

9. Blood laboratory test and imaging test

A. Blood laboratory test

none

B. Imaging test

- 1) A quantitative MR angiography (QMRA) with noninvasive optimal vessel analysis (NOVA) for the changes of cerebral blood flow.
- 2) A brain MRI including FLAIR for the presence of new cerebral ischemic lesions.

10. Subject discontinuation (Drop-out)

- 1) Difficulty in administration of study drugs.
- 2) Impossible to follow up.

11. Patient data safety

Any identifiable human material and data will be excluded in the research. And a subject will be given a subject number. Collected data will be managed with a password by only the principle investigator and investigators. The data will be discarded after 3-year mandatory storage period.

12. Audit

The principle investigator will carry out inspections at finishing data collection and at

finishing data analysis.

13. Statistical analysis

The results will be analyzed in intention-to-treat method. For analysis of primary outcome, Fisher's exact test will be used for a dichotomized variable.

14. Detailed study schedule

Visits	Screening baseline	1 st F/U (Telephone/ OPD visit)	2 nd F/U (Telephone/ OPD visit)	3 rd F/U (Telephone/ OPD visit)	4 th F/U (Telephone/ OPD visit)
Date	0 day	1 month (± 2 weeks)	3 months (± 2 weeks)	6 months (± 2 weeks)	12 months (± 2 weeks)
Obtaining consent	●				
MR	●				●
Drug compliance		●	●	●	●

15. References

4) Lee CH, Kim J-H. A review on the medicinal potentials of ginseng and ginsenosides on cardiovascular diseases. *J Ginseng Res.* 2014;38:161-166

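### Section 10 counts difficulty taking study drug as drop-out without saying that reachable patients stay in follow-up, which Sections 7D and 13 need

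*Combined protocol and SAP*

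**What the plan says.** Section 10, on subject discontinuation, has a heading that equates discontinuation with drop-out and two entries: "Difficulty in administration of study drugs" and "Impossible to follow up". It gives no further rule.

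On follow-up, 7D states: "Both groups will be followed up at 1, 3, 6 and 12 months after randomization". It adds that at each follow-up, besides the primary outcome history, "any adverse effects, any co-administration drugs, and study drug compliance will be evaluated". The Section 8 compliance form sets expected days of administration against "Actual administration days", and its medication form has a field for the date the drug ended.

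On the mode of contact, Section 8 says: "The follow-ups can be conducted in outpatient clinics or by telephone interview performed by experienced nurses". It names stroke or TIA history and mRS as the items covered in the interview. 7B, however, describes the second primary outcome as assessed by "aggravation of patient status (mRS, modified Rankin Scale) at out-patient clinic during one-year follow-up". 7G adds a diffusion MRI when an event is reported, and Section 14 places an MR at 12 months.

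On analysis, Section 13 says: "The results will be analyzed in intention-to-treat method", with Fisher's exact test for the dichotomised primary outcome. It does not define the analysis set further or say how a patient without a one-year outcome enters the test.

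**The concern.** Section 10 is the only place that classifies a patient who has trouble with the capsules, and it classifies that patient as a drop-out. Loss of contact has its own entry, so the first entry is not just another name for it. Site staff could reasonably take it as grounds to stop contacting someone who would still answer the telephone.

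Such losses would arise after randomisation, for a reason connected with treatment. If they differed between arms, the comparison would lose part of the balance that intention-to-treat is meant to protect. If they did not differ, outcomes would still be missing in a trial of 29 per arm with no stated drop-out allowance. With no rule in Section 13, the handling of those patients could also be settled after the data are seen. Some of this loss is avoidable, because telephone contact is already permitted for stroke or TIA history and mRS.

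**Working it through.** **1. The passages side by side.**

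| Question | Section 10 | 7D, 8 and 14 | 13 |
|---|---|---|---|
| Is a reachable patient off drug a drop-out? | Yes, by the first entry | Not addressed | Not addressed |
| Do that patient's contacts continue to 12 months? | Not stated | Both groups are followed; off-drug patients are not mentioned | Intention-to-treat needs the outcome |
| How is a missing one-year outcome handled? | Not stated | Not stated | Not stated |

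The conflict is conditional. It arises if drop-out is taken to end follow-up, and no passage says whether it does.

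**2. The plan's own figure.** Inputs from 7C are proportions 0.1 and 0.4, alpha 0.05, power 0.8 and 1:1 allocation. I take alpha as two-sided. The unpooled formula gives n = (1.960 + 0.842)² × (0.1×0.9 + 0.4×0.6) / 0.3² = 28.78, rounded up to 29 per group. This matches the plan. 7C mentions no allowance for drop-out.

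**3. Illustration of missing outcomes.** The documents give no drop-out rate, so I assume 1 or 2 missing outcomes per arm. Observed events are the whole numbers nearest the planned proportions:

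- 28 observed per arm: 0.1×28 = 2.8 and 0.4×28 = 11.2, so 3 and 11.
- 27 observed per arm: 0.1×27 = 2.7 and 0.4×27 = 10.8, so 3 and 11.

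The two-sided Fisher p is the sum of the probabilities of all tables with the same margins that are no more likely than the observed one. I computed it on the observed patients, then on all 29 per arm for every possible outcome of the missing patients.

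*One missing per arm* (3/28 vs 11/28, p = 0.029):

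| Ginseng events of 29 | Placebo 11 | Placebo 12 |
|---|---|---|
| 3 | 0.029 | 0.015 |
| 4 | 0.070 | 0.038 |

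The range is 0.015 to 0.070, with 3 of 4 combinations below 0.05.

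*Two missing per arm* (3/27 vs 11/27, p = 0.028):

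| Ginseng events of 29 | Placebo 11 | Placebo 12 | Placebo 13 |
|---|---|---|---|
| 3 | 0.029 | 0.015 | 0.007 |
| 4 | 0.070 | 0.038 | 0.020 |
| 5 | 0.141 | 0.082 | 0.045 |

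The range is 0.007 to 0.141, with 6 of 9 combinations below 0.05.

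**4. Sensitivity to the assumed counts.** With one more placebo event, the picture is milder. For 12/28, one missing per arm gives 0.007 to 0.038, with all 4 combinations below 0.05. For 12/27, two missing per arm gives 8 of 9 below 0.05.

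**5. How likely the extremes are.** Suppose the missing patients have events at the planned 0.1 and 0.4. With one missing per arm, only 4 vs 11 is above 0.05; its probability is 0.1×0.6 = 0.06, so 94% stays below. With two missing, the combinations above 0.05 are 4 vs 11 (0.18×0.36 = 0.0648), 5 vs 11 (0.01×0.36 = 0.0036) and 5 vs 12 (0.01×0.48 = 0.0048). They total 0.073, so about 93% stays below.

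**6. Timing.** This version is dated March 02, 2018, and Section 5 ends the study on July 31, 2018. Assume that all last visits fall by then. With the 2-week window, the latest randomisation is August 14, 2017. That patient's 6-month visit is due February 14, 2018, and its window closes February 28, 2018. On that assumption, every 1, 3 and 6 month window had closed before this version was dated.

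**The case against.** A reader might infer that Section 10 removes these patients from the study, or that the protocol abandons intention-to-treat. The text does not support that. Section 10 never says that visits stop, that data are excluded or that outcomes go unrecorded. 7D is unconditional about both groups, compliance is checked at every contact to month 12, the forms allow for incomplete dosing, and Section 13 names intention-to-treat. Together these favour continued follow-up. That part of the objection stands and limits the point to an unresolved conflict. It does not close the gap: recording partial compliance shows that missed doses were expected, not that contact continues once a patient is called a drop-out.

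A reader might also infer that the arms will lose patients unequally. The documents do not show this. The capsules look identical and carry the same daily burden (7E), and patients with past adverse effects of ginseng are not eligible (6A). The size and direction of any bias cannot be derived.

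The figures are open to challenge too. They move with the assumed counts, equal weight on every combination overstates fragility, and missing outcomes from unreachable patients have the same effect. All of this stands, so the figures show only that a few missing outcomes can matter.

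Finally, telephone contact does not cover everything. 7B places the mRS-based outcome at the clinic, and the diffusion MRI and the 12-month MR need attendance.

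**Conclusion.** The point holds in a limited form and should be corrected. It is more than a missing detail, because Section 10 actively assigns the drop-out label to patients who may be reachable, while 7D and Section 13 depend on their outcomes.

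That one or two missing outcomes per arm can carry p across 0.05 rests on assumed numbers missing, assumed event counts and a two-sided test. It is not a forecast: at the planned rates, most of the probability stays below 0.05. It also does not isolate drug-related drop-out from other loss, and the fix can prevent only the part that involves reachable patients. Confidence is medium, since the protocol can be read in the milder way.

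**What to change.** **Section 10.** Define two separate states, study drug stopped and withdrawn from follow-up, without changing when drug is stopped. State that patients off drug keep their remaining scheduled contacts, with telephone allowed for stroke or TIA history and mRS. State that they are invited to the planned 12-month MR unless they refuse or cannot be reached. Reconcile this with the clinic-based wording of the second primary outcome in 7B.

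**Section 13, before unblinding.** State that all randomised patients are analysed in their assigned arm and that events recorded before withdrawal count. State that the number with missing outcomes is reported per arm, and that Fisher's test is repeated from best to worst case for each primary outcome. Counting lost patients as event-free should not be prescribed as the only main rule: it can understate event rates and can mislead if losses differ by arm.

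**Cost.** The change needs wording in two sections. The contacts and the MR are already in the Section 14 schedule. The estimate will include time off drug and may be smaller than the on-drug effect. Contacts already missed by March 02, 2018 cannot be restored. A 12-month contact that is still open can ask about the whole year, subject to recall, and the Section 13 wording needs no new visits.

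### The primary Fisher test makes no use of acute-ischemic-lesion status on the data form; it is valid, but with 58 patients its power depends heavily on how such a factor falls between the arms

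*Combined protocol and SAP*

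**What the plan says.** - **Analysis (Section 13).** The analysis is by intention to treat, and "For analysis of primary outcome, Fisher's exact test will be used for a dichotomized variable". No covariate, stratum or adjusted analysis is named.
- **Allocation (Section 7.D).** Patients are allocated "by 1:1 ratio according to random permuted block with a block size of 20". No stratification factor is named.
- **Sample size (Section 7.C).** "Assuming the proportion of 0.1 in the ginseng group and the proportion of 0.4 in placebo group", the "calculated sample size would be 29 patients each group", or 58 in total.
- **Data form (Section 8).** The first table has a column headed "The presence of acute ischemic lesions", in the same row as sex, age and the catheter-angiography findings. It carries no time label. The NOVA, FLAIR and stroke-history tables do carry time labels, so baseline is a fair inference from position, but it is an inference.

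The documents nowhere call lesion status prognostic, and they do not give its frequency.

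**The concern.** The primary outcome is stroke or TIA within one year. A patient who enters with a fresh ischemic lesion may well have a different risk from one who does not. With 29 per arm and no stratification, the arms can differ noticeably in the share of such patients. An unstratified two-by-two test cannot separate that difference from a treatment effect: an excess in the ginseng arm hides a real benefit, and an excess in the placebo arm inflates it. If the item is already collected, stratifying the same kind of exact test on it removes most of this dependence without a single extra patient. What is at stake is robustness and some power, not overall type I error.

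**Working it through.** **1. The plan's own figure.** With alpha 0.05 (read as two-sided, since Section 7.C calls it an equality test), power 0.8 and unpooled variance:

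n = (1.960 + 0.842)² × (0.1×0.9 + 0.4×0.6) / 0.3² = 28.8, rounded up to 29 per arm. The stated size reproduces.

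**2. Power of the planned test.** Exact enumeration of two binomials (29, 0.1) and (29, 0.4) gives Fisher power of 0.681. At a common risk of 0.25 its actual size is 0.024, so it is conservative. Expected events: 29×0.1 + 29×0.4 = 14.5.

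**3. How often imbalance arises.** Treat the number of carriers per arm as independent binomial (29, prevalence). Prevalence is an assumption, because the documents give none.

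| Assumed prevalence | Difference of 6 or more, either direction | Ginseng excess of 6 or more |
|---|---|---|
| 20% | 7.0% | 3.5% |
| 30% | 11.4% | 5.7% |
| 50% | 14.8% | 7.4% |

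**4. What imbalance does.** Assume 50% prevalence and placebo risks of 0.6 with a lesion and 0.2 without.

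- Average placebo risk: 0.5×0.6 + 0.5×0.2 = 0.4.
- Odds ratio of the factor: (0.6/0.4)/(0.2/0.8) = 6.
- A common treatment odds ratio of 0.134 gives ginseng risks of 0.168 and 0.032, which average 0.10.

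Expected crude risks:

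- 17 ginseng vs 11 placebo carriers: ginseng (17×0.168 + 12×0.032)/29 = 0.112; placebo (11×0.6 + 18×0.2)/29 = 0.352. The difference shrinks to 0.24.
- 11 vs 17: ginseng (11×0.168 + 18×0.032)/29 = 0.084; placebo (17×0.6 + 12×0.2)/29 = 0.434. The difference grows to 0.35.

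Power by exact enumeration. The stratified test refers total ginseng events to the convolution of the two stratum hypergeometric distributions, two-sided by probability ordering.

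| Carriers, ginseng vs placebo | Fisher | Stratified exact |
|---|---|---|
| 17 vs 11 | 0.47 | 0.75 |
| 14 vs 14 | 0.68 | 0.72 |
| 11 vs 17 | 0.85 | 0.74 |

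**5. Average gain, and where it comes from.** Simulation with 20,000 trials per scenario, 29 per arm, marginal risks held at 0.1 and 0.4, and assumed prevalence of 20%, 30% and 50%. The last column compares the Cochran-Mantel-Haenszel test with the unadjusted chi-square test. Neither carries Fisher's discreteness penalty, so the difference isolates the covariate.

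| Assumed odds ratio of the factor | Fisher | Stratified exact | Gain, points | Covariate alone, points |
|---|---|---|---|---|
| 1 | 0.68 | 0.71–0.72 | 3.0–3.2 | −0.5 to −0.4 |
| 2 | 0.68 | 0.72–0.73 | 3.7–4.4 | 0.0–0.5 |
| 3 | 0.68–0.69 | 0.73–0.74 | 4.8–5.5 | 1.0–1.6 |
| 5 | 0.68 | 0.75–0.76 | 6.8–7.8 | 3.4–3.8 |
| 10 | 0.68–0.69 | 0.78–0.80 | 10.5–11.7 | 6.5–7.2 |

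The first row shows that about 3 points are gained even when the factor is unrelated to outcome. That part is reduced discreteness. The two parts come from different tests, so they need not add up exactly to the gain.

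**6. Type I error.** At a common risk of 0.25, prevalence 30% and odds ratios of 3, 5 and 10, Fisher rejects in 2.4–2.6% of trials overall and the stratified exact test in 3.2–3.4%. Given an imbalance of 6 or more in either direction, Fisher rejects in 4.0%, 4.8% and 7.5%, and the stratified test in 3.3%, 3.2% and 2.8%.

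**The case against.** The case for leaving Section 13 alone has four parts.

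- **Validity.** After randomization an unadjusted test needs no covariate. Its overall type I error stays well below 0.05, and imbalance helps as often as it hurts: the mirror case gives 0.85. This stands. What remains is that the result depends on an avoidable accident of allocation.
- **Power can be raised without a covariate.** An unstratified Boschloo exact test reaches 0.776 at 29 per arm with size held below 0.05. That matches or beats the stratified exact test's average power for odds ratios of 1 to 5. This also stands, so average power alone is not the reason to stratify. Like any unstratified two-by-two test, however, Boschloo's does not correct for imbalance.
- **The choice of factor is a judgment.** The form also lists age, sex, stenosis severity and occlusion, and the documents do not rank them. Lesion status is the closest to the outcome, but with about 15 expected events only one factor, or at most two, can be carried. The choice must be made in advance.
- **Timing.** Section 7.G calls for a diffusion-weighted MRI when symptoms are reported during follow-up, and the form's column is unlabelled. If such a finding entered the column, stratifying on it would condition on post-randomization information. This stands as a condition on the fix.

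**Conclusion.** The point holds as a worthwhile improvement, not as a flaw that invalidates the plan. The planned test has power of 0.68 at the plan's own risks. Under the assumed 0.6/0.2 split, that power moves between about 0.47 and 0.85 with an imbalance of 6 carriers, while the stratified exact test stays near 0.75. An imbalance at least that large, in either direction, occurs in about 7% to 15% of trials for assumed prevalence of 20% to 50%. The average gain is about 3 to 12 points over assumed odds ratios of 1 to 10, with the covariate itself worth about 0 to 7.

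Two stronger readings are tempting, and neither is supported.

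- A reader might infer that ignoring lesion status costs this trial 3 to 13 points of power. The documents give neither input needed for such a statement. The lower end is Fisher's discreteness. The upper end (0.82 vs 0.68–0.69) needs placebo risks of 0.7 and 0.1, an odds ratio of (0.7/0.3)/(0.1/0.9) = 21.
- A reader might infer that chance imbalance makes the Fisher test invalid. Over all randomizations it does not. In the scenarios run, the rate passes 5% only conditionally, at an odds ratio of 10.

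Stratification also does not by itself settle the separate gap between the planned 0.8 and 0.68. Fisher would need 36 per arm to reach 0.80.

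**What to change.** Before unblinding:

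1. In Section 13, make the primary test the exact conditional test stratified by acute ischemic lesion status recorded before randomization (yes/no). Report the common odds ratio with its exact interval.
2. Keep the unstratified test as a prespecified sensitivity analysis.
3. In Section 8, label the lesion column as baseline and state how the lesion is ascertained, so that no MRI finding after randomization can enter it.

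The cost is a sentence or two in Section 13, one column label and standard exact software. No new patients are needed, and no new data if the column is indeed completed at baseline; confirm that first. There are two small downsides. The estimate becomes a conditional odds ratio, and the trial commits in advance to one factor whose prognostic strength the documents do not establish. If the factor proves unrelated to outcome, the stratified exact test still had slightly more average power than Fisher in the scenarios run (0.71–0.72 vs 0.68).

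### The stated power of 0.8 at 29 per group does not belong to the planned Fisher's exact test, whose power there is 0.68

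*Combined protocol and SAP*

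**What the plan says.** Section 7.B defines primary outcome (i), ischemic stroke or TIA, as a count of patients: "during one-year follow-up and measured by number of patients in each group".

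Section 7.C sizes the trial on two proportions, "Assuming the proportion of 0.1 in the ginseng group and the proportion of 0.4 in placebo group", with alpha 0.05, power 0.8 and 1:1 allocation, and concludes that the "calculated sample size would be 29 patients each group". It names an equality test but gives no formula, no sidedness and no allowance for drop-out.

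Section 13 adopts intention-to-treat and says that, for the primary outcome, Fisher's "exact test will be used for a dichotomized variable". It names no effect estimate or confidence interval, and no rule for a patient whose one-year status is unknown.

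Section 10 lists "Impossible to follow up" among the reasons for discontinuation, so such patients are foreseen.

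Sections 7.D and 14 place contacts at 1, 3, 6 and 12 months. The Section 8 form has columns for 3, 6, 9 and 12 months, for example "The presence of any ischemic stroke history at 6 months follow-up". Its column titles name ischemic stroke but not TIA.

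**The concern.** A power figure is only meaningful for the test that will be run. Fisher's exact test is known to be conservative in small samples, and about 14.5 events are expected here (29 × 0.1 + 29 × 0.4). If 29 came from a formula for a different test, the trial is more likely to miss the effect it was designed to detect than the plan admits.

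Loss to follow-up could widen the gap. A patient last seen event-free at 6 months has no one-year status. A yes/no table might leave that patient out, count the patient as event-free, or use imputed or later retrieved status, and the plan does not say which. Counting such patients as event-free pulls the two observed proportions together.

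Conservatism protects against a false positive. What is at stake is a missed effect, and a negative result that would be read as if the trial had had 80% power.

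**Working it through.** **Inputs.** Proportions 0.1 and 0.4, alpha 0.05, power 0.8 and 29 per group are from Section 7.C; the test is from Section 13. Two-sided testing is assumed, because it reproduces the plan's figure. Drop-out of 0%, 10% and 20% is assumed, because the plan gives no rate.

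**1. The plan's own figure.** The unpooled normal-approximation formula is

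n = (z₀.₉₇₅ + z₀.₈₀)² × [p₁(1−p₁) + p₂(1−p₂)] / (p₂−p₁)²

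= (1.960 + 0.842)² × (0.09 + 0.24) / 0.09 = 28.8, so 29.

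Nominal power at 29 by the same formula is 0.803. Other formulas do not give 29: pooled variance 32, continuity-corrected 38, one-sided pooled 25.

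**2. Power of the planned test.** Let X₁ ~ Bin(29, 0.1) and X₂ ~ Bin(29, 0.4). Sum P(X₁=a) × P(X₂=b) over all tables (a, b) whose two-sided Fisher p-value is at most 0.05. The result is **0.681**. Nearby sizes:

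| Per group | 29 | 32 | 35 | 36 |
|---|---|---|---|---|
| Fisher power | 0.681 | 0.748 | 0.785 | 0.800 |

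**3. Where the loss comes from.** The same enumeration with equal proportions in both arms gives Fisher's true size: 0.009 at a common rate of 0.10, and never above about 0.025 at any common rate. About half or more of the nominal 0.05 goes unused. Other tests on the same yes/no counts at 29 per group:

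| Test | Power, 0.1 vs 0.4 | Maximum size |
|---|---|---|
| Fisher | 0.681 | 0.025 |
| Boschloo (exact) | 0.776 | 0.048 |
| Pearson chi-square | 0.778 | not bounded by construction |

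Changing only the test recovers 0.776 − 0.681 = 0.095, with no use of event timing.

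**4. Drop-out and event timing.** This step is a simulation, with exponential event times matching 0.1 and 0.4 at 12 months and drop-out unrelated to stroke risk. Events are dated only to the first completed contact at 1, 3, 6 or 12 months. Both binary tests count lost patients as event-free.

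| Assumed drop-out | Fisher | Boschloo | Log-rank |
|---|---|---|---|
| 0% | 0.68 | 0.77 | 0.78 |
| 10% | 0.63 | 0.73 | 0.75 |
| 20% | 0.58 | 0.70 | 0.73 |

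The log-rank margin over Boschloo is 0.01, 0.02 and 0.03. These figures move by 0.01 to 0.03 with the simulation run, the drop-out model and the dating of events; log-rank at 20% ranged from 0.71 to 0.74. If Fisher is instead applied only to patients with known status, its power is about 0.68 at 10% and 0.65 at 20% drop-out.

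**The case against.** A tempting stronger reading is that the yes/no analysis throws away partial follow-up, and that a log-rank test on first event would gain about 0.1 in power from the same patients. The documents' figures do not support that. With complete follow-up nothing is discarded, yet Fisher is already at 0.68, and a better binary test closes nearly all of the gap. Timing adds about 0.01 to 0.03.

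A reader might also infer that log-rank should become the primary test. Section 7.B defines the outcome as a number of patients and Section 7.C sizes it on proportions, so a two-proportion test is coherent with both. Log-rank would change the quantity being compared and would still not reach 0.80.

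Nor do the documents say that lost patients will be counted as event-free. That handling is one possibility. Section 8 allows telephone follow-up, so some one-year statuses could be retrieved, and imputation is another option. The drop-out figures are illustrations under assumed rates.

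In the plan's defence, Fisher's test is valid, familiar and never exceeds its nominal level. The version is also late: it is dated March 02, 2018, and the study is expected to end on July 31, 2018, so any new event-date field would be filled in largely retrospectively.

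What stands is narrower. The stated power is not the power of the stated test, and this follows from the plan's own figures at zero drop-out.

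**Conclusion.** The point holds as a mismatch between the sample-size formula and the test. Stated power is 0.8. Actual power is 0.68 with complete follow-up, and 36 rather than 29 per group would be needed for 0.80 with Fisher. This part rests only on the plan's proportions, group size and alpha, with two-sided testing.

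The further fall to about 0.63 and 0.58 depends on assumed drop-out of 10% and 20% and on counting lost patients as event-free. The log-rank figures also assume constant hazards and non-informative censoring. The shortfall is mainly due to Fisher's conservatism; unused event timing is a minor contributor. None of the tests considered reaches 0.80 at 29 per group.

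**What to change.** 1. **Section 7.C:** state the power for the test actually used. For Fisher at 29 per group with complete follow-up this is 0.68.
2. **Section 13:** replace Fisher with a less conservative exact test on the same counts, such as Boschloo's (power 0.776, maximum size 0.048). Report the risk difference with a 95% CI, and state how patients with unknown one-year status enter the table.
3. **Section 13:** add a supportive time-to-first-event analysis, with log-rank and Kaplan-Meier 12-month risks and drop-outs censored at the last completed contact. Where no date is known, use the contact at which the event was first reported.
4. **Sections 7.D, 8 and 14:** before item 3, reconcile the contact months (3/6/9/12 on the form, 1/3/6/12 elsewhere), and make clear that the form captures TIA as well as stroke.

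The cost is analysis wording and a form correction, with no extra patients or visits. The downsides are a less familiar test, power still slightly below 0.80 (which should be stated), and a censoring assumption in the supportive analysis. Given the document date, the change of test should be recorded as made before treatment codes are opened; if that is no longer possible, keep Fisher as primary, label the alternative as supportive, and still correct the power statement.
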